## 1.0 Summary of Study

Peripheral nerve blocks catheters of the femoral nerve have long been used for perioperative analgesia in total knee arthroplasty (TKA). These blocks provide effective analgesia and patient satisfaction for surgical pain relief. However, one of the main drawbacks to the femoral nerve block (FNB) is a denser motor block of the quadriceps muscle that can delay aggressive physical therapy and subsequent recovery from surgery. (1) Recently, there has been increasing interest in performing adductor canal blocks (ACB) with the aim of less motor blockade while providing commensurate analgesia compared to the FNB. (1,2) Current investigative reports have provided only preliminary data, and there is potential to change the standard of care for TKA as more data mounts in favor of ACBs. The goal of this study is to verify the analgesic equivalence of the two blocks, compare patient satisfaction, surgeon satisfaction, and physical therapy grading between the two blocks. Potentially, this would change the standard of care for TKA patients at this institution.

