## 2.0 Background and Rationale

Femoral nerve block catheters have been used to provide analgesia for lower extremity procedures for many years. The catheter is placed near the femoral nerve and a continuous infusion provides a dense nerve block in the distribution of the femoral nerve. This includes blockade of the anterior and posterior divisions supplying the middle cutaneous, medial cutaneous, and muscular (sartorius) branches in the anterior division and the saphenous, muscular (to quadriceps) and articular branches of the posterior division. In particular, the muscular branch supply to the quadriceps makes walking and participating in physical therapy difficult.

A block in the adductor canal can be expected to include the saphenous nerve, vastus medialis, medial femoral cutaneous, articular branches from the obturator and the medial retinacular nerves. This distribution provides the innervation for the medial, anterior and lateral portions of the knee. Van der Wal et al first demonstrated in 1993 the transsartorial approach to blocking the saphenous nerve.(4) In recent years, the ACB has been proposed as a potential successor to the FNB. (1,2,3,5) Kwofie et al investigated quadriceps strength and fall risk in volunteers finding that ACB significantly preserved motor strength and significantly preserved balance. ACB also demonstrated superior analgesia compared to parenteral opioids alone. Further, Kim et al performed a prospective, randomized, controlled trial comparing ACB to FNB with the end point of quadriceps strength, reported analgesia, and opioid intake showing that ACB provided similar analgesia while with less motor block.

This study has been designed to increase the knowledge concerning adductor canal block for total knee arthroplasty surgery as a potentially superior replacement for femoral nerve blocks. Previous studies have well demonstrated the preservation of quadriceps strength and balance. Analgesia also appears to be adequate. This study seeks to replicate those findings with the addition of assessment of physical therapy participation, patient satisfaction, surgeon satisfaction and time to discharge.

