### **4.0 Objectives and Hypothesis**

Following are the specific objectives of this study:

1. Determine the effectiveness of ACB for analgesia compared to FNB as determined by patient reported VAS scores
2. Determine the effectiveness of ACB for analgesia compared to FNB as determined by opioid usage
3. Determine the effectiveness of ACB in physical therapy as determined by early ambulation distance
4. Determine surgeon satisfaction via survey.
5. Determine if there is any difference in time to discharge between the two blocks.

Outline of therapy: Participants in the investigational group will receive an adductor canal nerve catheter prior to TKA surgery. Participants in the control group will receive a femoral nerve catheter prior to TKA surgery. After surgery, the patient will be seen in the recovery room to bolus the catheters and start continuous infusions of ropivacaine. Further details are below in section #

Following are primary endpoints:

1. Pain scores (VAS) at immediate post op, 24 hours, and 48 hours, including highest
2. Opioid consumption at 24 hours and 48 hours pain score at any given time post operatively.
3. Physical therapist assessment of patient participation 0-100.
4. Distance ambulated at 24 hours and 48 hours
5. Patient satisfaction
6. Surgeon satisfaction
7. Hours to discharge.

Study Hypothesis: We hypothesize that the ACB will become the standard of care for TKA analgesia on the basis of improved physical therapy participation and increased patient satisfaction without sacrificing analgesia. With better physical therapy participation, there would be quicker recovery and potentially earlier discharge, increasing patient and surgeon satisfaction.

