## 8.0 Statistical Considerations

**General Data Analysis:** All demographic and clinical variables with continuous measures will be expressed as means and standard deviations; categorical factors will be expressed as proportions. For non-normal data, the medians and inter quartile ranges will be displayed. The distribution of the continuous factors will be examined using the Kolmogorov-Smirnov test. For data that are normally distributed, the one-way ANOVA and Student's t-test will be used to compare groups of data. For data that are not normally distributed, the Kruskal-Wallis and Mann-Whitney tests will be used for comparisons. Chi-square and Fisher's exact tests will be used to analyze categorical data. For all comparisons, a value of  $p < 0.05$  will be considered statistically significant.

**Primary Outcome Analysis:** Statistical analyses will be performed using SAS for Windows, version 9.2. Student's t-test will be used to compare post-operative pain scores for investigational and control subjects. Linear regression will be also be used to test the relationship between pain scores and regional anesthetic technique, while controlling for relevant clinical and demographic variables. Distance of first ambulation will be analyzed using Cox proportional hazards model. Student's t-test will be used to compare patient and surgeon satisfaction.

**Statistical Power and Sample Size Estimates:** Sample size (100) was determined using a Cohen's d table assuming a mean pain VAS score of 8 ( $sd = 3$ ) on a scale of 0-10 for control subjects. A sample of 100 participants (50 patients per treatment group) will have approximately 80% power to detect a reduction in pain score of at least 50%, and approximately 99% to detect an 80% reduction in pain score.

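### The stated goal is analgesic equivalence, but pain is analysed and sized only for a difference, with no margin or confidence-interval rule

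*Combined protocol and SAP*

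**What the plan says.** **The aim.** Section 1.0: "The goal of this study is to verify the analgesic equivalence of the two blocks". It adds: "Potentially, this would change the standard of care for TKA patients at this institution". The hypothesis in section 4.0 expects the adductor canal block (ACB) to prevail over the femoral nerve block (FNB) through "improved physical therapy participation and increased patient satisfaction without sacrificing analgesia". Other wording differs. The numbered objectives in section 4.0 are neutral, for example "Determine the effectiveness of ACB for analgesia compared to FNB as determined by opioid usage", and section 2.0 calls ACB "a potentially superior replacement for femoral nerve blocks".

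**The analysis.** Section 8.0, Primary Outcome Analysis: "Student's t-test will be used to compare post-operative pain scores for investigational and control subjects". A covariate-adjusted linear regression of pain on block type is added. Section 8.0 sets significance at p < 0.05 for all comparisons and does not state sidedness. The General Data Analysis paragraph of the same section has a broader rule: "The distribution of the continuous factors will be examined using the Kolmogorov-Smirnov test", and "For data that are not normally distributed, the Kruskal-Wallis and Mann-Whitney tests will be used for comparisons".

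**The sample size.** Section 8.0 assumes a control VAS mean of 8 (SD 3, scale 0-10). It claims about 80% power for a 50% reduction in pain and about 99% for an 80% reduction, with 50 patients per group.

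Nowhere in the supplied text is there a margin, an interval-based decision rule or a pair of one-sided tests, either for VAS or for opioid use.

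**The concern.** A test of difference can reject equality. Failing to reject it shows only that the data are compatible with no difference, and they may be equally compatible with a worsening that matters. The sizing also looks the other way: it asks whether pain falls, while the case for ACB needs evidence that pain does not rise.

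The stakes follow from the protocol's own argument. ACB is to be preferred because rehabilitation improves while pain relief is kept, and the result might alter local practice. The rehabilitation half can be tested by a difference. The pain half has no rule by which it could be concluded, so a non-significant p-value could fill the gap after the fact.

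**Working it through.** **Inputs.** Control mean 8, SD 3, scale 0-10 and 50 per arm are from section 8.0. Assumptions: SD 3 in both arms unless stated, no dropout, two-sided 5% test. The documents give no margin, so 1.0, 1.5, 1.7 and 2.0 points are illustrative only.

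**1. The plan's own power figure.** SE = 3 × √(2/50) = 0.60.
- Read literally, 50% of 8 is 4 points and 4/0.60 = 6.67, so power is above 99.9%, one- or two-sided, not 80%.
- The stated pair is matched by standardised effects of 0.5 (1.5 points) and 0.8 (2.4 points) in a one-sided 0.05 test: 0.799 and 0.990. Two-sided gives 0.697 and 0.977.

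On either reading the target is a difference. The mismatch itself is a separate error in section 8.0, and this point does not depend on it.

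**2. Precision.** With 98 degrees of freedom, t is 1.984 for a 95% interval and 1.661 for a 90% interval. Half-widths are 1.984 × 0.60 = 1.19 and 1.661 × 0.60 = 1.00 points.

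**3. What a non-significant result leaves open when the true difference is 0.** Let D be the observed difference, ACB minus FNB. The trial is non-significant if |D| < 1.19. The upper 95% limit exceeds 1.0 if D > 1.0 − 1.19 = −0.19, and exceeds 1.5 if D > 1.5 − 1.19 = 0.31. In the normal approximation:
- above 1.0: [Φ(1.985) − Φ(−0.318)] / [2Φ(1.985) − 1] ≈ 0.601/0.953 = 0.63
- above 1.5: [Φ(1.985) − Φ(0.515)] / 0.953 ≈ 0.280/0.953 = 0.29

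Allowing for the estimated SD gives 0.628 and 0.293.

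**4. A real worsening that the test would miss.** Take control mean 8 and SD 3, with ACB one point worse and ACB SD 2. SE = √(9/50 + 4/50) = 0.51 and 1/0.51 = 1.96, so the trial is non-significant about 51% of the time (57% if the ACB SD is 2.5).

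**5. Power of 50 per arm if a margin were set, true difference 0.** Non-inferiority is concluded if the upper two-sided 95% limit lies below the margin (noncentral t, noncentrality margin/SE). Equivalence uses two one-sided tests (TOST) at 0.05 each, that is, a 90% interval wholly inside ± the margin. SE is 0.60, 0.50 and 0.40 at SD 3, 2.5 and 2.

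| Illustrative margin | Non-inferiority, SD 3 | Non-inferiority, SD 2.5 | Non-inferiority, SD 2 | TOST, SD 3 |
|---|---|---|---|---|
| 1.0 | 38% | 51% | 70% | 4% |
| 1.5 | 70% | 84% | 96% | 60% |
| 2.0 | 91% | 98% | 99.9% | 90% |

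The margin at which non-inferiority power reaches 80% is 1.70 at SD 3, 1.41 at SD 2.5 and 1.13 at SD 2. With an assumed 10% dropout (45 per arm) and SD 3, non-inferiority power at 1.0/1.5/2.0 falls to 35/65/88%.

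**6. The ceiling.** If the control mean is 8, the ACB mean cannot exceed 10. A margin of 2.0 then excludes nothing (8 + 2.0 = 10), and 1.7 would accept an ACB mean up to 9.7. This holds only under the assumed mean of 8 and SD of 3.

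**The case against.** The strongest reply is that equivalence is a loose word used once, in a summary. The numbered objectives are neutral, the background speaks of possible superiority, and the remark about standard of care is conditional. The t-test and regression also yield an interval for the mean difference, so the information exists. Much of this is fair, and if only estimation is intended, a wording change is enough. But section 1.0 calls equivalence the goal and the section 4.0 hypothesis needs pain to be no worse. An interval without a margin fixed beforehand can be called equivalent afterwards whatever its width.

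Four stronger readings are tempting, and the documents do not support them:
- **The investigators will read p ≥ 0.05 as equivalence.** No section says so. The plan leaves that open; it does not prescribe it.
- **One hundred patients are too few.** This is not shown. The SD of 3 is a planning assumption for controls, and power changes markedly with the SD and the margin.
- **Pain will be moved to Mann-Whitney and no interval will exist.** The general paragraph of section 8.0 would allow the switch, but the more specific primary-outcome paragraph names the t-test without a normality condition. The text does not settle which governs.
- **Any adequately powered margin is trivial because of the ceiling.** At a lower control mean or a smaller SD the argument weakens or disappears.

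**Conclusion.** The concern stands and needs correction before analysis. Followed as written, the plan has no valid route from its pain analysis to the conclusion named in section 1.0 or to the pain half of the section 4.0 hypothesis. The defect is the missing margin and decision rule, not a proven shortfall in sample size.

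The size of the gap at SD 3, 50 per arm and no dropout is that a non-significant result would commonly leave a worsening of a point or more unexcluded. The precision figures rest on the protocol's own SD, and the margin-power figures also rest on margins chosen here for illustration. The uncertainty over which test governs pain is a secondary ambiguity to clear up at the same time.

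**What to change.** Before data are seen:

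1. Pre-specify a clinically justified VAS margin at one named time point. Do not choose it to fit 100 patients, and check it against the 0-10 ceiling at the expected control mean.
2. State the rule. Conclude non-inferiority only if the upper limit of the two-sided 95% interval for mean VAS (ACB minus FNB) is below the margin, or equivalence only if the 90% interval lies wholly within ± the margin.
3. State that this t-based or regression-based interval decides the matter whatever the normality test shows, with Mann-Whitney as supportive only. Name the analysis set, and say whether opioid use is supportive or has its own margin.
4. Restate the power of 100 patients for that margin over a range of SDs.
5. If no defensible margin is adequately powered, drop the equivalence claim, report the difference with its 95% interval, and do not treat p ≥ 0.05 as equivalence.
6. Align sections 1.0, 4.0 and 8.0 with the choice.

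**Cost.** Wording and agreement on a margin; no new data items and no required change in N. Re-sizing is open only if enrolment allows. As a guide, 80% non-inferiority power at a 1-point margin and SD 3 needs 2 × [3 × (1.960 + 0.842)/1.0]² ≈ 142 per arm. The downside is that the trial can then formally fail to show equivalence or non-inferiority, and the stated power may look less favourable than it does now.

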## 2.0 Background and Rationale

Femoral nerve block catheters have been used to provide analgesia for lower extremity procedures for many years. The catheter is placed near the femoral nerve and a continuous infusion provides a dense nerve block in the distribution of the femoral nerve. This includes blockade of the anterior and posterior divisions supplying the middle cutaneous, medial cutaneous, and muscular (sartorius) branches in the anterior division and the saphenous, muscular (to quadriceps) and articular branches of the posterior division. In particular, the muscular branch supply to the quadriceps makes walking and participating in physical therapy difficult.

A block in the adductor canal can be expected to include the saphenous nerve, vastus medialis, medial femoral cutaneous, articular branches from the obturator and the medial retinacular nerves. This distribution provides the innervation for the medial, anterior and lateral portions of the knee. Van der Wal et al first demonstrated in 1993 the transsartorial approach to blocking the saphenous nerve.(4) In recent years, the ACB has been proposed as a potential successor to the FNB. (1,2,3,5) Kwofie et al investigated quadriceps strength and fall risk in volunteers finding that ACB significantly preserved motor strength and significantly preserved balance. ACB also demonstrated superior analgesia compared to parenteral opioids alone. Further, Kim et al performed a prospective, randomized, controlled trial comparing ACB to FNB with the end point of quadriceps strength, reported analgesia, and opioid intake showing that ACB provided similar analgesia while with less motor block.

This study has been designed to increase the knowledge concerning adductor canal block for total knee arthroplasty surgery as a potentially superior replacement for femoral nerve blocks. Previous studies have well demonstrated the preservation of quadriceps strength and balance. Analgesia also appears to be adequate. This study seeks to replicate those findings with the addition of assessment of physical therapy participation, patient satisfaction, surgeon satisfaction and time to discharge.

### **3.0 Significance of Study**

This study has the potential to add to the growing body of evidence that the ACB will eventually be the superior regional anesthetic technique in total knee arthroplasty patients. At this institution, both blocks are currently performed, but the ACB could become the primary technique.

### **4.0 Objectives and Hypothesis**

Following are the specific objectives of this study:

1. Determine the effectiveness of ACB for analgesia compared to FNB as determined by patient reported VAS scores
2. Determine the effectiveness of ACB for analgesia compared to FNB as determined by opioid usage
3. Determine the effectiveness of ACB in physical therapy as determined by early ambulation distance
4. Determine surgeon satisfaction via survey.
5. Determine if there is any difference in time to discharge between the two blocks.

Outline of therapy: Participants in the investigational group will receive an adductor canal nerve catheter prior to TKA surgery. Participants in the control group will receive a femoral nerve catheter prior to TKA surgery. After surgery, the patient will be seen in the recovery room to bolus the catheters and start continuous infusions of ropivacaine. Further details are below in section #

Following are primary endpoints:

1. Pain scores (VAS) at immediate post op, 24 hours, and 48 hours, including highest
2. Opioid consumption at 24 hours and 48 hours pain score at any given time post operatively.
3. Physical therapist assessment of patient participation 0-100.
4. Distance ambulated at 24 hours and 48 hours
5. Patient satisfaction
6. Surgeon satisfaction
7. Hours to discharge.

Study Hypothesis: We hypothesize that the ACB will become the standard of care for TKA analgesia on the basis of improved physical therapy participation and increased patient satisfaction without sacrificing analgesia. With better physical therapy participation, there would be quicker recovery and potentially earlier discharge, increasing patient and surgeon satisfaction.

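### Seven endpoints are all called primary and every comparison is tested at p < 0.05, with no lead endpoint, order, adjustment or success rule

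*Combined protocol and SAP*

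**What the plan says.** Section 4.0 (Objectives and Hypothesis) heads its list "Following are primary endpoints". The list covers pain VAS, opioid consumption, therapist-rated participation, distance ambulated, patient satisfaction, surgeon satisfaction and hours to discharge. No endpoint is called secondary. The hypothesis in the same section is a joint one: better participation and satisfaction, with no loss of analgesia.

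In Section 8.0 (Statistical Considerations), General Data Analysis says that p < 0.05 in any comparison "will be considered statistically significant". Sidedness is not given.

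The Primary Outcome Analysis paragraph covers several endpoints together:

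- **Pain:** a t-test "will be used to compare post-operative pain scores for investigational and control subjects", with no time point. In addition, "Linear regression will be also be used to test the relationship between pain scores and regional anesthetic technique", adjusted for covariates. The plan does not say which decides.
- **Ambulation:** "Distance of first ambulation will be analyzed using Cox proportional hazards model".
- **Patient and surgeon satisfaction:** a t-test.

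Only pain is sized. The sample-size paragraph gives 50 per arm about 80% "power to detect a reduction in pain score of at least 50" per cent, again with no time point.

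**The concern.** Section 1.0 says that the results might change the institution's standard of care, so a reader needs to know which result would support the adductor canal block. The plan leaves at least two readings open.

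- **Any one primary endpoint suffices.** A nominal 5% per test then does not hold the overall false-positive rate at 5%.
- **The whole hypothesis must hold.** Multiplicity is then not the problem, but the pain component needs a test that can show preserved analgesia. Section 1.0 also names analgesic equivalence as the goal. A difference test cannot show either, because a non-significant result may only reflect limited precision.

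**Working it through.** **1. The plan's own power figure.** Inputs from Section 8.0: control mean 8, SD 3, 50% reduction, 50 per arm.

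- Difference = 0.5 × 8 = 4 points, or 4/3 = 1.33 SD.
- Standard error = 3 × √(2/50) = 0.60; 4/0.60 = 6.67.
- Two-sided power at 0.05 is about Φ(6.67 − 1.96) = Φ(4.71), which exceeds 99.99%. The t-test calculation agrees.

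The stated 80% is not reproduced. With 50 per arm, a two-sided t-test has 80% power for 0.57 SD (0.566), which is 0.566 × 3 = 1.7 VAS points.

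**2. The number of comparisons.**

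| Endpoint | Count from the list | Uncertainty |
|---|---|---|
| Pain VAS | 4 | The fourth, highest score, has to be pieced together from items 1 and 2 |
| Opioids | 2 | Section 7.0 item d calculates 24-hour use only, which gives 1 |
| Participation | 1 | – |
| Distance | 2 | Section 8.0 and Appendix C refer to first ambulation, which gives 1 |
| Patient satisfaction | 1 | 2 if both 24 h and 48 h are tested |
| Surgeon satisfaction | 1 | Section 7.0 item h asks for a general impression; Appendix D has three items per patient |
| Hours to discharge | 1 | – |

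The list gives 4 + 2 + 1 + 2 + 1 + 1 + 1 = 12. One opioid and one distance comparison give 10. One test per endpoint gives 7. The remaining ambiguities could move the count further either way.

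**3. Chance of at least one false positive if any one counts.** Two-sided 0.05 per test is assumed.

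- Independent tests: 1 − 0.95^k.
- Common correlation ρ, normal statistics: 1 − ∫ φ(x) [Φ((1.96 − √ρ·x)/√(1−ρ)) − Φ((−1.96 − √ρ·x)/√(1−ρ))]^k dx, by numerical integration.

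| k | Independent | ρ = 0.3 | ρ = 0.5 | ρ = 0.7 |
|---|---|---|---|---|
| 7 | 30% | 27% | 23% | 18% |
| 10 | 40% | 35% | 29% | 21% |
| 12 | 46% | 40% | 32% | 23% |

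Even at ρ = 0.9, seven tests give 11%.

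**4. The joint reading.** SD 3, 50 per arm, two-sided t-test at 0.05 with 98 degrees of freedom. For an assumed true worsening of 1 point, the noncentrality is 1/0.60 = 1.67 and the critical value is 1.98. The result is non-significant 62% of the time. For 0.5 and 1.5 points the figures are 87% and 30%.

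**5. The price of adjusting all seven.** Holm compares the smallest p-value with 0.05/7 = 0.0071. At that threshold, with 50 per arm, power for 0.566 SD falls from 80% to 53%. About 80 per arm would restore 80%.

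**The case against.** The best defence is that pain is the implicit lead: it is listed first and is the only endpoint sized. Both facts are right, but the plan does not draw that conclusion. The Primary Outcome Analysis also covers ambulation and satisfaction. Pain has several time points with none chosen, and two analyses with no deciding one. The hypothesis also rests on function and satisfaction rather than on lower pain.

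A second defence is that a joint hypothesis does not inflate error. That is sound in principle. The plan does not make the hypothesis its decision rule, however, and with a difference test the pain component would remain unproven.

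Third, this is a minimal-risk comparison of two techniques already in use, intended to add to existing evidence, so formal adjustment is partly convention. That stands, and it limits how serious the point is.

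Two stronger readings go beyond the documents:

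- A reader might infer that the trial has a 46% false-positive rate. That needs exactly 12 independent tests and an any-one-counts rule. The count is soft, the endpoints are plausibly correlated, and no such rule is written.
- A reader might combine the 62% with assumed gains in participation and satisfaction to get a wrong-success rate for the joint hypothesis. That needs a rule that non-significance means preserved analgesia, a margin that makes 1 point unacceptable, and effect sizes for the other endpoints. The plan gives none of these.

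**Conclusion.** The concern holds as a missing decision rule. If any one primary endpoint counts, the false-positive rate is several times the nominal 5%. If the whole hypothesis must hold, the planned pain test cannot support its analgesia component.

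Confidence is high that no rule is written. It is moderate for the magnitudes, which rest on an uncertain count, assumed two-sided testing, assumed correlations and, for the 62%, an assumed 1-point worsening. This should be corrected before analysis; it does not invalidate the randomised comparison.

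**What to change.** **Preferred.** Before analysis, name one primary endpoint, at one time point, with one deciding analysis, and state whether the test is two-sided. Relabel the other six as secondary, reported with 95% confidence intervals and no confirmatory claim. The choice is the sponsor's:

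- **Pain VAS:** say whether the t-test or the regression decides.
- **Ambulation distance** (the third objective: "Determine the effectiveness of ACB in physical therapy as determined by early ambulation distance"): first reconcile first ambulation with the 24 h and 48 h distances.
- **Participation** (listed as "Physical therapist assessment of patient participation 0-100"): first reconcile the scale. Section 7.0 has 0–10 for the investigational arm and 0–100 for the control arm, and Appendix C has 1 to 10.

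**Alternative.** Keep seven primaries with one prespecified test each and apply Holm, accepting the power loss in step 5.

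**In either case.** Any claim of preserved or equivalent analgesia needs a non-inferiority or equivalence test with a margin that the sponsor justifies. For scale, a non-inferiority test at one-sided 2.5% (SD 3, 50 per arm, equal true means) has 38% power for an illustrative 1-point margin and reaches 80% only at about 1.7 points.

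**Cost.** The preferred option costs wording and the primary status of six endpoints. Power or precision must be restated under every option, including pain superiority, because the current 80% does not follow from its inputs. For distance and participation the plan gives no SD or target difference. For a continuous endpoint analysed by t-test, 50 per arm gives 80% power for 0.57 SD and a 95% confidence-interval half-width of 1.98 × √(2/50) = 0.40 SD.
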